6.2.4. Analysis of Primary Endpoint

To address the primary endpoint, we will use a Fisher's exact test to calculate the likelihood that a difference in detectable SARS-CoV-2 between a given dose of study drug (EIDD-2801 400 mg up to 800 mg) versus placebo, occurs by chance. Because the current SARS-CoV-2 RNA test is only 70% sensitive, we will perform 2 NP swabs at baseline and 2 NP swabs on Day 5, each analyzed separately (4 total NP swab measurements). Thus, an undetectable result at a given time point will be determined when neither NP swab has detectable (below the LOD of the assay) viral RNA at that time point. To graphically present the results, we will show individual points and smoothed curves to fully account for individual negative tests that are contemporaneously observed with positive tests.

6.2.5. Analysis of Secondary Endpoints

Secondary Virologic Endpoints:

- 1. Time to clearance of viral RNA in NP swabs
 - by qPCR
- 2. The decline in viral RNA by Day 3, Day 5, Day 8, Day 11, Day 15, Day 19, and Day 28 after initiation of study drug in NP swabs
 - - by qPCR
- 3. Rate of decline in viral RNA (change in log10 copies/mL per day) in NP swabs
 - - by qPCR

The time to clearance of viral RNA will be analyzed using the Kaplan-Meier method. The event time of median, 25th, 75th percentiles and associated 95% confidence intervals will be provided by dose group. The cumulative probability of BLOQ and the associated 95% confidence interval for the scheduled visit will also be provided by dose group.

The decline in viral RNA over time will be analyzed using a mixed effect of repeated measure model (MMRM). The model estimated between-group differences and associated 95% confidence intervals will be provided by scheduled visits. The rate of decline for each dose group will be estimated using a mixed effect linear model.

Additional details will be described in a SAP and finalized before database lock.

Details for the analyses of exploratory virologic endpoints will be described in the SAP.

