4.3.3. Virologic Assessments

Upon enrollment, participants will have 2 NP swabs performed, one in each nostril (R or L to be documented), accessing the posterior nasopharynx. The NP swabs will be collected and stored separately for laboratory analysis. On Days 3, 5, 8, 11, 15 (inpatients only), 19 (inpatients only), and 28, participants will also have 2 NP swabs performed in the same way, collected and stored identically and individually. One swab will be sent to an infectivity lab for analysis. The other swab will be sent to for PCR sequencing. Detailed instructions for preparation and shipment of samples will be provided in a separate document.

Version: 7.0

Version: 7.0 18 May 2021

In the setting of bronchoalveolar fluid lavage with sampling, or in participants who require mechanical ventilation who have endotracheal tube fluid sampling, we will collect a portion to perform viral RNA testing and the infectivity assay on the sample. If available from SOC procedures, a sample of sputum will also be collected if the participant has a productive cough and used to perform viral RNA testing and infectivity assays. In addition, a portion of material from NP swabs will be archived and frozen for viral sequencing.

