4.3.4. Clinical Assessments

On each day that virology samples are obtained, participants will be assessed for clinical endpoints and interim AEs (and SAEs). Chart review will occur on structured days to perform safety assessments and record concomitant medications (including antivirals). CMP, CBC with differential, and urinalysis will be recorded at regular intervals during the study as indicated in the Schedule of Events (see Section 7.1). Any results that are not available will be obtained on the applicable chart extraction day.

Participants who are discharged from the hospital during study participation will return to the clinic for study visits through the Day 28 visit. Clinic visits will occur on Days 3, 5, 8, 11, and 28. On Day 15 (± 1 day), a member of the study staff will contact the participant by telephone to query them about symptoms, study drug adherence, and concomitant medications. Outpatients will be seen in one of several locations, including but not limited to COVID-19 ambulatory pods, COVID-19 ambulatory clinics and clinical research units, and home visits. In all cases, visits will conform to infection control practices that are established by the institution. If the participant is discharged to a secondary care facility, study site staff will take measures to meet institutional regulatory requirements of the primary site as well as the receiving site to continue collecting study-related samples where allowed.

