6.2.2. Data Handling

Day 1 is defined as the day of first dose of study drug. Relative days after Day 1 are calculated as (assessment date – Day 1 date) + 1. Relative days prior to Day 1 are calculated as (assessment date – Day 1 date). The day prior to Day 1 is Day -1.

All data will be analyzed using nominal study visits as defined in the Study Schedule and eCRF. No visit windows will be applied for summary and analysis. Unscheduled visits will be listed but not tabulated.

Participants who received the same dose (i.e., placebo) across study parts will be combined into the same dose group. Data from the active treatment arms may be combined for analysis, when appropriate in comparison with the pooled placebo group.

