Targeted physical examination ^k	X	X	X	X		X	X
Laboratory ¹	X	X	X	X		X	X
Chest radiography ^m	X	X	X	X		X	X

Abbreviations: AE = adverse event; BAL = bronchoalveolar; BID = twice daily; CBC = complete blood count; CMP = complete metabolic panel; ECG = electrocardiogram; EOS = end of study; ICU = intensive care unit; IL-6 = interleukin 6;

; $MR = medical \ record$; NP = nasopharyngeal; PBO = placebo; PK = pharmacokinetic; $QD = once \ daily$; $QOD = every \ other \ day$; $SOE = schedule \ of \ events$; $WHO = World \ Health \ Organization$.

- a. For participants who are discharged from the hospital after randomization and administration of the first-dose of study drug or PBO, this schedule will apply. Day number will be counted from enrollment. Participants will enter the Outpatient SOE upon day of discharge. Outpatients will be seen in one of several locations, including but not limited to COVID-19 ambulatory pods, COVID-19 ambulatory clinics and clinical research units, and home visits. In all cases, visits will conform to infection control practices that are established by the institution.
- b. If Day 5 falls on a Saturday, then a visit will occur on Day 4. If Day 5 falls on a Sunday, then a visit will occur on Day 6.

- c. Serology testing will be performed on plasma for IL-6 levels on Day 1 (pre-dose), Day 5 and Day 28, and specimens will be archived for further cytokine testing in the future.
- d. Pregnancy test is required for women of childbearing potential only. High sensitivity serum pregnancy tests are required on Day 28. Additional serum or urine pregnancy tests may be performed, as determined necessary by the investigator or required by local regulation, to establish the absence of pregnancy at any time during the subject's participation in the study.
- e. Phone calls will be used to query participants about symptoms, study drug adherence, concomitant medications and to assess WHO ordinal scale.

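### Kaplan-Meier estimates of RNA clearance at Days 15 and 19 run late by an amount that depends on discharge, because discharged participants have no swab between Day 11 and Day 28

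*Protocol*

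**What the plan says.** **Analysis.** Protocol 6.2.5 states: "The time to clearance of viral RNA will be analyzed using the Kaplan-Meier method". It asks for the median and quartiles by dose group and adds: "The cumulative probability of BLOQ and the associated 95% confidence interval for the scheduled visit will also be provided by dose group". Section 6.2.2 fixes the time scale: "All data will be analyzed using nominal study visits as defined in the Study Schedule and eCRF". No interval-censored method is named. Further detail is left to the SAP, which is not at hand.

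**Swab days.** Section 4.3.3: "On Days 3, 5, 8, 11, 15 (inpatients only), 19 (inpatients only), and 28, participants will also have 2 NP swabs performed". For discharged participants section 4.3.4 says: "Clinic visits will occur on Days 3, 5, 8, 11, and 28". Their Day 15 contact carries no swab: "a member of the study staff will contact the participant by telephone to query them about symptoms, study drug adherence, and concomitant medications". The outpatient table in 7.1 agrees, with NP swabs on Days 3, 5, 8, 11 and 28.

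**What decides the schedule.** A footnote to the outpatient table: "Participants will enter the Outpatient SOE upon day of discharge". Another footnote allows a swab on the day of discharge, at the investigator's discretion in consultation with the sponsor.

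**The concern.** A swab series shows only that clearance lies between the last positive and the first negative swab. Kaplan-Meier on nominal visits puts the event at the right-hand end of that interval. This does little harm when everyone has the same swab days. Here the interval after Day 11 is 4 days or 17 days according to whether the participant is still in hospital. Two participants who both clear on Day 12 are recorded on Day 15 (inpatient) and Day 28 (discharged).

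Discharge follows randomisation and could be affected by treatment; days of hospitalization is itself an exploratory endpoint. At stake are the Day 15 and Day 19 points of the clearance curve for the first secondary virologic endpoint, and the median or upper quartile when these fall after Day 11.

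**Working it through.** **The plan's own figures.** The protocol gives no figure for time to clearance. Its only power figure is 83% for the Day 5 primary endpoint (6.1: 80% v 20% detectable). Exact enumeration of a two-sided Fisher test with 14 v 14 gives 83.7%, which supports this reading of the planning rates. Those rates are used below.

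**1. Gaps after Day 11.** Inpatient: 15 − 11 = 4 days. Discharged: 28 − 11 = 17 days. The outpatient windows (±1 day on Day 11, ±2 on Day 28) make that 26 − 12 = 14 to 30 − 10 = 20.

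**2. What Kaplan-Meier reads.** Let F(d) be the true share cleared by day d, and h15 and h19 the shares still inpatient on Days 15 and 19. Assume a perfect assay, no dropout, discharge independent of clearance, and a Day 28 swab for all.
- Days 3, 5, 8, 11 and 28: reads F(d), which is correct.
- Day 15: F(11) + h15 × [F(15) − F(11)].
- Day 19: the Day 15 value + h19 × [F(19) − F(15)].

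**3. Placebo planning rate (80% detectable at Day 5).** Exponential clearance from Day 1 is an assumption. The rate is −ln(0.80)/4 = 0.0558 per day, so the true median is Day 1 + ln 2/0.0558 = Day 13.4. F(11) = 0.428, F(15) = 0.542, F(19) = 0.634, F(28) = 0.778. Thus 57% are still detectable at Day 11.

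| Discharged by Day 11 (rest stay inpatient) | Day 19 reads | Kaplan-Meier median |
|---|---|---|
| 0% | 0.634 | Day 15 |
| 50% | 0.428 + 0.5 × 0.206 = 0.531 | Day 19 |
| 80% | 0.428 + 0.2 × 0.206 = 0.469 | Day 28 |
| 100% | 0.428 | Day 28 |

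True clearance is the same in every row.

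**4. Two arms with identical clearance but different discharge.** None of these inputs is in the protocol: Weibull clearance, shape 1.3, median 12 days after Day 1; lognormal discharge, log-scale SD 0.6, median m = Day 8 or Day 12.
- F(d) = 1 − 2^(−((d − 1)/12)^1.3): F(11) = 0.421, F(15) = 0.571, F(19) = 0.691, F(28) = 0.863.
- Share still inpatient = 1 − Φ(ln(d/m)/0.6). For m = 8: h15 = 0.147, h19 = 0.075. For m = 12: h15 = 0.355, h19 = 0.222.
- Day 19, m = 8: 0.421 + 0.147 × 0.150 + 0.075 × 0.120 = 0.452.
- Day 19, m = 12: 0.421 + 0.355 × 0.150 + 0.222 × 0.120 = 0.501.
- Split of the shortfall: 69.1 − 50.1 = 19.0 points in both arms; 50.1 − 45.2 = 4.9 points more in the earlier-discharged arm.

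With a true median of 10 days, Day 19 reads 53% v 58% against 77%. If everyone had a discharge-day swab, the 12-day case would read 47% v 53% against 69%.

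**5. Faster clearance.** At 60% detectable on Day 5 (exponential), the median stays at Day 8, but Day 19 reads 90% if all stay inpatient and 72% if all are discharged, against a true 90%. At the planned active rate of 20%, the rate is −ln(0.20)/4 = 0.402 and exp(−0.402 × 10) = 0.018. Only 1.8% are still positive at Day 11, so little can be misplaced.

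**6. Does interval censoring remove the bias?** Exponential data with identical clearance in both arms were fitted by a likelihood using (last positive, first negative]. The mean estimated hazard ratio was 0.97 to 1.03 over every discharge split tried. This fit was parametric and took discharge as independent of clearance.

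**The case against.** **The SAP may settle it.** No sentence says that the visit day counts as the exact clearance day; that is inferred from Kaplan-Meier plus nominal visits. The unseen SAP could define event times differently or add an interval-censored analysis. This is fair as far as it goes. But the protocol itself fixes the estimator, the per-visit output, nominal visits and the discharge-dependent swab days. A SAP that follows it reproduces the distortion.

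**A reader might infer that the whole endpoint is biased against a working drug.** The documents do not support that. Days 3 to 11 share one schedule, and Day 28 catches up. The between-arm part needs discharge to differ by arm, on which the protocol gives no figures. At the planned active rate it is negligible.

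**A reader might quote medians of Day 28 v Day 19 from step 4.** That is a knife-edge result: the later-discharged arm reads 50.1% at Day 19. With a true median of 12.2 or 13 days both arms read Day 28; with 8 or 9 days both read Day 11. The Day 19 probability is the steadier measure.

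**The size is modest against the noise.** With about 14 per arm, the standard error at 50% is √(0.5 × 0.5/14) = 13 points. In simulations with identical clearance, 14 or 28 per arm and 80–90% v 30–40% discharged, a log-rank test rejected against the earlier-discharged arm in 4% to 7% of runs (nominal 2.5%). The protocol names no such test. This limits the weight of the point but does not make the Day 15 and Day 19 estimates right.

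**Between-arm contrast and deaths.** One might add that 6.2.5 gives no between-arm comparison for this endpoint and no rule for deaths before clearance. Both are ordinary SAP content and form no part of this point.

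**Conclusion.** The point holds in limited form. Followed as written, the Kaplan-Meier estimates at Days 15 and 19, and any quartile falling after Day 11, run late by an amount set by discharge.

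At the placebo planning rate the Day 19 estimate can lie anywhere from 63% to 43% for the same true clearance. In the two-arm illustration, about 19 points of shortfall are common to both arms and about 5 are bias against the earlier-discharged arm. These sizes rest on the assumed clearance and discharge distributions and on discharge being independent of clearance. The 4-day and 17-day gaps come directly from the protocol.

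The Day 5 primary endpoint is untouched. This is a cheap improvement to a secondary analysis and does not threaten the trial's main conclusion.

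**What to change.** In 6.2.5, do one of the following:
- Analyse time to clearance as interval-censored between the last positive and the first negative swab, with a Turnbull estimate by dose group.
- Keep Kaplan-Meier but truncate it at Day 11, the last swab day both schedules share before they diverge. Report no Kaplan-Meier probabilities for Days 15 and 19, and give quartiles not reached by Day 11 as not reached.

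The change is to wording only, with no new visits or samples. The first option gives wider intervals and still assumes that swab timing is uninformative about clearance. The second gives up any time-to-clearance statement beyond Day 11.

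The Day 28 swab also needs reconciling: 4.3.3 lists it without an inpatient restriction, but the inpatient table in 7.1 shows none. If the table is followed, an inpatient still positive at Day 19 is censored there, while a discharged participant can still have an event on Day 28.

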6.2.6. Analysis of Adverse Event Data

Analysis of AE data will primarily be descriptive based on the DAIDS table for Grading the Severity of Adult and Pediatric Adverse Events, July 2017, version 2.1. Adverse events will be coded using the Medical Dictionary for Regulatory Activities (MedDRA). An AE is considered treatment-emergent if it begins or worsens in severity after the first dose of randomized study drug. The number and percentage of participants with treatment-emergent AEs will be tabulated by system organ class (SOC) and preferred term. Additional AE summaries will be provided by severity, drug related AEs, AEs leading to study drug discontinuation, and serious AEs.

6.2.7. Analysis of Other Safety and Clinical Data

Other safety and clinical endpoints will be provided descriptively by dose group and scheduled time of assessment where appropriate. Details will be provided in the SAP.

Version: 7.0

6.2.8. Analysis of Pharmacokinetic Data

Plasma EIDD-1931 PK Endpoints:

- 1. Maximum EIDD-1931 concentration (C_{max})
- 2. 1.5-hour EIDD-1931 concentration (C_{1.5})
- 3. 3-hour EIDD-1931 concentration (C₃)
- 4. Area under the concentration: time curve EIDD-1931 (AUC₀₋₈)
- 5. Elimination half-life (t_{1/2}) EIDD-1931

PBMC EIDD-2061 PK Endpoints:

- 1. Maximum EIDD-2061 concentration (C_{max})
- 2. EIDD-2061 time of maximal concentration (t_{max})
- 3. Elimination half-life of EIDD-2061 (t_{1/2})
- 4. Area under the concentration: time curve EIDD-2061 (AUC₀₋₁₂)
- 5. Parent: metabolite (Plasma EIDD-1931:PBMC EIDD-2061) concentration ratio at each time point

PK data will be summarized by dose group and scheduled time of assessment where appropriate. If data permit, assessment of dose proportionality will be performed and the relationship between the exposure parameters and virologic endpoints will be explored. Details will be described in the SAP.

Version: 7.0

7. STUDY PROCEDURES

7.1. Schedule of Events

Inpatient											
Study Procedures	Screening ^a Day -2 to 1	Day 1	Day 3	Day 4	Day 5	Day 8	Day 11	Day 15	Day 19	Day 28 (EOS)	Early Discontin- uation
Informed Consent	X										
Demographic data	X										
Inclusion/Exclusion Criteria	X										
Randomization ^b		X									
Medical History	X										
Pregnancy test ^c	X									X	X
Serology (plasma) ^d		Xe			X				X		
Height, weight, BMI	X										
Study residency											
Visit while hospitalized for MR review	X	X	X		X	X	X	X	X	X	X
Prior/Concomitant medication review	X	X	X		X	X	X	X	X		
Study drug vs. placebo											
EIDD-2801 or PBO		BID on	BID on	BID on	BID on						
administration		Days 1-5	Days 1-5	Days 1-5	Days 1-5						
Virologic endpoints											
NP swabs ^g		Xe	X e		X e	X	X	X	X		
BAL and/or sputum ^h		X	X		X	X	X	X	X		
Clinical endpoints											
WHO Ordinal Scale (Appendix 1) ⁱ		Xi	X		X	X	X	X	X	X	X
Clinical assessments ^j		X	X		X	X	X	X	X	X	X
Safety and tolerability											
AE/SAE reporting		X	X		X	X	X	X	X	X	X
Vital signs (temperature, blood pressure, pulse, respiratory rate)	X	X	X		X	X	X	X	X	X	X
Pulse oximetry ^k	X	X	X		X	X	X	X	X	X	X
Full physical examination	X			1						X	
Targeted physical examination ¹		X	X		X	X	X	X	X		X
Laboratory ^m	X		X		X	X		X	X		

Inpatient											
Study Procedures	Screening ^a Day -2 to 1	Day 1	Day 3	Day 4	Day 5	Day 8	Day 11	Day 15	Day 19	Day 28 (EOS)	Early Discontin- uation
12-lead ECG ⁿ	X						1 1	osttreatme	nt ECG to 1	pe performed, as fe	asible ⁿ
Chest radiography ^o		X	X		X	X	X	X	X	X	X
Pharmacokinetics											
Plasma ^p			X	X		·					
PBMCs ^p			X	X							

Abbreviations: AE = adverse event; BAL = bronchoalveolar lavage; BID = twice daily; CBC = complete blood count; CMP = complete metabolic panel; ECG = electrocardiogram; EOS = end of study; h = hours; ICU = intensive care unit; IL-6 = interleukin 6;

MR = medical record; NP = nasopharyngeal; PBMC = peripheral blood mononuclear cell; PBO = placebo; PK = pharmacokinetic; QD = once daily; QOD = every other day; SARS-CoV-2 = severe acute respiratory syndrome-coronavirus-2; SOE = schedule of events; WHO = World Health Organization.

- a. Screening and Day 1 procedures will occur on the same day whenever possible as soon as SARS-CoV-2 testing is determined to be positive. A window of up to 6 days is allowable if the participant has not had symptoms for more than 7 days prior to dosing.
- b. Randomization can happen at Screening or Day 1
- c. For women of child-bearing potential only, high sensitivity serum pregnancy tests are required at Screening within 24 hours of the first dose of study drug and on Day 28. Additional serum or urine pregnancy tests may be performed, as determined necessary by the investigator or required by local regulation, to establish the absence of pregnancy at any time during the subject's participation in the study.
- d. Serology testing will be performed on plasma for immune response on Day 1 (pre-dose), Day 5, and Day 19, and specimens will be archived for further cytokine testing in the future.
- e. The sample should be collected pre-dose.
- f. EIDD-2801 and PBO are to be administered BID on Days 1-5. The first dose will be administered in the morning of Day 1, if possible. If the first dose is given later in the day, the second dose may be given at least 4 hours later on Day 1. If the first dose on Day 1 is given in the late evening, the second dose may be taken on the morning of Day 2, in which case the final dose will be taken on the morning of Day 6. In the event of missed doses, if the total number of missed doses is 4 or fewer, the number of days of study drug can be extended by no more than 1 day (through Day 6) for the equivalent of missed doses up to 2 doses. If the participant misses more than 4 consecutive doses, or more than 5 total doses, then the participant will be discontinued from any further study drug administration and followed for safety for the remainder of the study.
- g. One NP swab will be collected from each nostril at each time point for a total of 2 swabs per time point.
- h. BAL and/or sputum fluid *may* be collected when available for viral RNA testing. No study specific interventions will be initiated for collection of BAL fluid and/or sputum if participant has a productive cough. If, during clinical care, BAL is performed and excess fluid is available, the study team will collect this fluid for testing.
- i. Note that on Day 1, the WHO ordinal scale assessment should be performed before the first dose of EIDD-2801 is administered.
- j. Clinical assessments will be ascertained by chart extraction and will include number of days in the hospital, maximum O₂ requirements daily, ICU admission and number of days in the ICU, mechanical ventilation and number of days requiring mechanical ventilation, death, and symptom reporting.

- k. Oxygen saturation is to be recorded twice daily (morning and evening) and may be ascertained by chart extraction; if not available in the participant's chart, it should be measured by the study staff.
- 1. Targeted physical examinations should be done if indicated by an AE or as needed in the judgement of the investigator.
- m. Laboratory measurements will include CBC with differentials, CMP (including amylase and lipase), and urinalysis.
- n. For ECGs, a single post-dosing recording should be collected. If the participant is discharged from the hospital before a post-dose ECG is recorded, and recording of an outpatient ECG is not feasible, then results of the last recorded ECG before hospital discharge will be entered into the CRF.
- o. Results of all chest radiography performed as part of routine clinical care during Study Days 1-28 should be recorded.
- p. Plasma and PBMC samples for PK analysis will be collected from participants if they are still inpatients on Day 3. Samples will be collected before the morning dose on Day 3 and at the following times after the Day 3 morning dose: 0.5 hours, 1.5 hours, 3 hours, 6 hours, 8 hours, and 24 hours (i.e., on the morning of Day 4). If a participant is scheduled to be discharged, then PK samples should be collected at all scheduled time points up to the time of discharge; in addition, if a participants is discharged prior to the 24-hour PK sample, a 12-hour PK sample should be collected, when possible. PK measurements will be assessed in participants enrolled at clinical sites able to conduct the collections. These sites include, but are not limited to,
 - be collected within a \pm 15 minute window (up to 3 hours), \pm 30 minutes (6-8 hours), or \pm 1 hour (12-24 hours).

	Outpatient ^a						
Study Procedures	Day 3	Day 5 ^b	Day 8 (±1 day)	Day 11 (±1 day)	Day 15 (±1 day)	Day 28 (EOS) (±2 days)	Early Discontin- uation
Serology (plasma) ^c		X				X	X
Pregnancy test ^d						X	X
Study residency							
Outpatient visit	X	X	X	X		X	X
Phone call ^e					X		
Study drug vs. placebo							
EIDD-2801 or PBO administration ^f	BID on Days 1-5	BID on Days 1-5					
Virologic endpoints							
NP swabs ^{g, h}	X	X	X	X		X	X
Clinical endpoints							
WHO Ordinal Scale (Appendix 1) ^h	X	X	X	X	X	X	X
Safety and tolerability							
Concomitant medication review	X	X	X	X	X	X	X
AE/SAE reporting h	X	X	X	X	X	X	X
Vital signs (temperature, blood pressure, pulse, respiratory rate) h	X	X	X	X		X	X
Pulse oximetry ^j	X	X	X	X		X	X
Targeted physical examination ^k	X	X	X	X		X	X
Laboratory ¹	X	X	X	X		X	X
Chest radiography ^m	X	X	X	X		X	X

Abbreviations: AE = adverse event; BAL = bronchoalveolar; BID = twice daily; CBC = complete blood count; CMP = complete metabolic panel; ECG = electrocardiogram; EOS = end of study; ICU = intensive care unit; IL-6 = interleukin 6;

; $MR = medical \ record$; NP = nasopharyngeal; PBO = placebo; PK = pharmacokinetic; $QD = once \ daily$; $QOD = every \ other \ day$; $SOE = schedule \ of \ events$; $WHO = World \ Health \ Organization$.

- a. For participants who are discharged from the hospital after randomization and administration of the first-dose of study drug or PBO, this schedule will apply. Day number will be counted from enrollment. Participants will enter the Outpatient SOE upon day of discharge. Outpatients will be seen in one of several locations, including but not limited to COVID-19 ambulatory pods, COVID-19 ambulatory clinics and clinical research units, and home visits. In all cases, visits will conform to infection control practices that are established by the institution.
- b. If Day 5 falls on a Saturday, then a visit will occur on Day 4. If Day 5 falls on a Sunday, then a visit will occur on Day 6.

- c. Serology testing will be performed on plasma for IL-6 levels on Day 1 (pre-dose), Day 5 and Day 28, and specimens will be archived for further cytokine testing in the future.
- d. Pregnancy test is required for women of childbearing potential only. High sensitivity serum pregnancy tests are required on Day 28. Additional serum or urine pregnancy tests may be performed, as determined necessary by the investigator or required by local regulation, to establish the absence of pregnancy at any time during the subject's participation in the study.
- e. Phone calls will be used to query participants about symptoms, study drug adherence, concomitant medications and to assess WHO ordinal scale.
- f. EIDD-2801 and PBO are to be administered BID on Days 1-5. The first dose will be administered in the morning of Day 1, if possible. If the first dose is given later in the day, the second dose may be given at least 4 hours later on Day 1. If the first dose on Day 1 is given in the late evening, the second dose may be taken on the morning of Day 2, in which case the final dose will be taken on the morning of Day 6. In addition, if a participant misses up to 2 doses during Days 1 to 5, dosing may be extended into Day 6. If discharge occurs prior to completion of study drug dosing (prior to Day 6), study drug will be administered in the hospital on the morning of discharge, and the remainder of the study drug will be dispensed for administration at home by the participant. Procedures will be put into place to ensure study drug compliance (e.g., telephone, eCollection) and drug accountability will be assessed on Days 5 and 8.
- g. One NP swab will be collected from each nostril at each time point for a total of 2 swabs per time point.
- h. Will be obtained at least once on the indicated day AND on the day of discharge from inpatient to outpatient, at the discretion of the investigator in consultation with the sponsor.
- i. Clinical assessments will be ascertained by chart extraction, including number of days in the hospital, maximum O₂ requirements daily, ICU admission and number of days in the ICU, mechanical ventilation and number of days requiring mechanical ventilation, death, and symptom reporting.
- j. If the oxygen saturation value is <92%, the measurement should be repeated once within 30 minutes.
- k. Targeted physical examinations should be done if indicated by an AE or as needed in the judgement of the investigator.
- 1. Laboratory measurements will include CBC with differentials, CMP (including amylase and lipase), and urinalysis.
- m. Results of all chest radiography performed as part of routine clinical care during Study Days 1-28 should be recorded.

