4. INVESTIGATIONAL PLAN

4.1. Definitions

- I. Enrolled: From time consented to initiation of study drug until designated as off study either through discontinuation or completion of the study.
- II. Randomized: when a patient identification (ID) number is assigned through randomization.
- III. Screen Failures: signed informed consent, but then determined to be ineligible or withdraws before initiation of study drug.
- IV. Discontinued: randomized, but then withdrawn by investigator or withdraws consent.
- V. Completed: Participants are considered completed when they are followed through to Day 28 or died before that.

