4.3. Intervention

4.3.1. Screening

Adult patients who are newly hospitalized with PCR-confirmed SARS-CoV-2 and evidence of symptomatic COVID-19 will be invited to participate in the study. Those who express interest will undergo the informed consent process and be given the chance to ask any questions before agreeing to participate. Those who consent to participate will undergo screening for study entry; the time between screening and study entry should be as short as possible (ideally the same day, but no longer than 48 hours). Screening assessments will include demographics, medical history, concomitant medications, review of inclusion and exclusion criteria, height, weight, BMI, physical examination including vital signs, clinical chemistry labs (CMP), hematology (CBC with differential), high sensitivity serum betahuman chorionic gonadotropin (HCG) (to rule out pregnancy) as applicable, urinalysis, electrocardiogram (ECG), and pulse oximetry. It is expected that measurements/values will have been obtained as SOC, and medical chart extraction will be performed. Missing values will be obtained as part of study procedures. Any chest radiography results from hospital admission will be recorded.

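### The protocol counts study day from first dose in 6.2.2 but from enrolment in the outpatient schedule, and with nominal-visit analysis a mistimed outpatient swab still counts as Day 5

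*Protocol*

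**What the plan says.** - **Anchor in the statistics section.** Section 6.2.2: "Day 1 is defined as the day of first dose of study drug". The study day of an assessment follows from it: "Relative days after Day 1 are calculated as (assessment date – Day 1 date) + 1". The primary objective (Section 1.1) also times Day 5 from the start of study drug.
- **Anchor for discharged participants.** Section 7.1, outpatient schedule, footnote a: "Day number will be counted from enrollment".
- **Meaning of enrolled.** Section 4.1: "Enrolled: From time consented to initiation of study drug until designated as off study either through discontinuation or completion of the study". The phrase names both consent and start of study drug.
- **Gap allowed before study entry.** Section 4.3.1 says of the time from screening to study entry: "ideally the same day, but no longer than 48 hours". The Protocol Summary gives a screening window of 0 to 2 days.
- **Weekend rule.** Outpatient footnote b: "If Day 5 falls on a Saturday, then a visit will occur on Day 4". A Sunday Day 5 moves to Day 6. The outpatient columns for Days 8, 11, 15 and 28 carry a tolerance; the Day 5 column carries none.
- **Analysis.** Section 6.2.2 uses nominal visits for all data and adds: "No visit windows will be applied for summary and analysis".

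**The concern.** Day 5 is the day of the primary endpoint, and the protocol allows two ways of finding it for anyone discharged by then. A site that takes footnote a together with the consent wording in Section 4.1 could swab an outpatient on the third day of dosing and label the visit Day 5. The weekend rule adds a further day in either direction. Because the analysis goes by visit label, these swabs are not distinguished from swabs taken on the true Day 5, and a swab on Day 6 can satisfy an endpoint defined as clearance by Day 5. The same labels feed the secondary rate of decline, which is expressed per day and so depends directly on correct timing, and time to clearance.

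This is not a detail left to the SAP: the conflicting anchors and the no-window rule are both in the protocol text.

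**Working it through.** **1. Day arithmetic.** Let *g* be the days from enrolment to first dose (0, 1 or 2, from Section 4.3.1 and the Protocol Summary) and *w* the weekend shift (−1 Saturday, 0 weekday, +1 Sunday, from footnote b). With the enrolment day as Day 1, the nominal Day 5 is enrolment + 4 days, the visit takes place at enrolment + 4 + *w*, and first dose is at enrolment + *g*. The formula in 6.2.2 then gives

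true study day = (4 + *w* − *g*) + 1 = 5 + *w* − *g*.

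| Enrolment to first dose | Saturday | Weekday | Sunday | Error in days |
|---|---|---|---|---|
| 0 days (enrolment = first dose) | 4 | 5 | 6 | −1 to +1 |
| 1 day | 3 | 4 | 5 | −2 to 0 |
| 2 days | 2 | 3 | 4 | −3 to −1 |

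Example of the extreme: enrolled Tuesday, first dose Thursday. The nominal Day 5 is Saturday, the visit moves to Friday, and Friday is Day 2 from first dose. If start days are spread evenly over the week (assumption), 2/7 = 29% of outpatient Day 5 visits move.

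**2. The plan's own power.** Section 6.1 assumes 14 v 14, with 80% of placebo and 20% of active participants detectable (so 20% and 80% undetectable), Fisher's exact test and α = 0.05, and states 83%. Exact enumeration, two-sided, gives 83.7%. The figure is reproduced.

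**3. Effect of mistimed swabs.** The protocol gives no clearance by day, so this step rests on assumptions: RNA falls 0.3 to 0.5 log10 per day, and the between-participant SD is 1.5 log10. For a swab shifted by *d* days,

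P(undetectable) = Φ(Φ⁻¹(p) + slope × *d* / SD).

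With slope 0.5 and *d* = −2 on active: Φ(0.842 − 0.667) = Φ(0.175) = 56.9%.

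| Shift | Active (80% on time) | Placebo (20% on time) |
|---|---|---|
| 1 day early | 69–74% | 12–15% |
| 2 days early | 57–67% | 7–11% |

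**4. Power, anchor effect.** Suppose 30 to 50% of all participants in both arms are swabbed two days early.
- Mildest case (30%, slope 0.3): active 0.7 × 80 + 0.3 × 67.1 = 76.1%; placebo 0.7 × 20 + 0.3 × 10.7 = 17.2%; difference 58.9 points; power 82.5%.
- Worst case (50%, slope 0.5): active 0.5 × 80 + 0.5 × 56.9 = 68.5%; placebo 0.5 × 20 + 0.5 × 6.6 = 13.3%; difference 55.2 points; power 79.3%.

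**5. Power, weekend rule alone.** Suppose 30 to 50% are outpatients, of whom 1/7 are one day early and 1/7 one day late. Clearance stays within 0.2 points of 80% and 20%, and power is 83.1 to 83.6%. Early and late shifts nearly cancel.

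**The case against.** The strongest reply is that enrolment in footnote a simply means Day 1. Footnote a applies only to participants who have already had a first dose. The dosing row of the same outpatient table runs over Days 1 to 5, with the first dose on Day 1. The inpatient schedule gives screening its own label, Day −2 to 1, so a consent date two days before dosing is not Day 1. Section 4.3.3 takes the baseline swabs upon enrolment, and the schedule puts those on Day 1 before dosing. This reading is plausible, and under it only the one-day weekend shift remains. What stands against it is that the literal text says otherwise and sites may differ.

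It is also fair that screening and dosing are meant to fall on the same day where possible. The shares of 30 to 50% in the working need that many participants both to use the full 48 hours and to be discharged by Day 5, which is pessimistic.

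A reader might infer that mistiming biases the comparison of arms, because discharge follows randomisation and the drug may affect it. If only the active arm were swabbed two days early, the model above would give power of 62 to 77%. Nothing in the protocol supports that case: the trial is double-blind, the gap from consent to first dose is fixed before treatment, and no discharge rates by arm are given. A reader might also infer that outpatient Day 5 swabs are routinely taken on dosing Day 3. The text permits this on one reading but does not require it.

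**Conclusion.** The point holds as an internal contradiction about the day of the primary endpoint, combined with an analysis rule that does not detect the result. On the literal reading an outpatient Day 5 swab can be two days early from the anchor and three with the Saturday rule; on the favourable reading it is at most one day early or late. Only participants discharged by the Day 5 visit are affected.

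The likely consequence is modest dilution and timing noise: a few points of power at most when both arms are affected alike, and almost none from the weekend rule. Those figures depend on the assumed slope, SD and share of participants. Directional bias between arms is possible but not shown. The case for acting is that the endpoint day should be uniquely defined and the correction is very cheap. Severity: minor to moderate.

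**What to change.** 1. In outpatient footnote a, count day number from the day of first dose (Day 1), in line with 6.2.2 and the primary objective.
2. In 6.2.2, use actual days from first dose as the time variable for the rate-of-decline and time-to-clearance analyses.
3. State that swabs on actual Days 4 to 6 count for the Day 5 endpoint, which is the spread the weekend rule produces once the anchor is first dose. State also how a swab outside that range is treated under 6.2.3, in particular whether it counts as missing and so as non-response.

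The cost is one footnote and two or three sentences. No new data are needed, because the relative-day formula in 6.2.2 already uses assessment and first-dose dates.
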